## 6.2 Safety Endpoints

Adverse events (AEs) are the only safety endpoints captured in this study.

# 7 Data Analysis and Statistical Considerations

Statistical summary tables and subject data listings will be prepared using SAS Version 9 or higher (SAS Institute, Cary, North Carolina, USA).

## 7.1 Analysis Populations

### 7.1.1 Safety Population

All subjects who have been entered into the Treatment Phase of the study and self-administered any treatment will be included in the Safety Population. A subject will be included in a treatment group for analysis based upon the treatment actually administered, rather than the group to which he or she has been assigned. For example, a subject who is randomized to receive placebo treatments but inadvertently receives active treatment will be included in the group receiving active treatment.

Should a subject gain access to their clinical trial materials and treat themselves without having called in to the clinic and been given permission to open their Treatment kit, that subject will also be included in the Safety Population if follow-up safety data are available.

The Safety Population will be used for all subject listings and for summary tables of the safety endpoints. No formal statistical analyses are planned for the safety endpoints.

### 7.1.2 Modified Intent-to-Treat (MITT) Population

All subjects who have been entered into the Treatment Phase of the study will be included in the modified intent-to-treat (MITT) Population. It is considered a “modified” intent to treat population in that it does not include all randomized subjects but includes only those randomized subjects who access their treatment, i.e., are told to open their kit. A subject will be included in a treatment group for analysis based upon the treatment to which he or she has been assigned; imputation on the primary endpoint only is planned for the MITT Population – see section 7.13. The MITT Population will be used as the primary analysis population and for all efficacy analyses.

### 7.1.3 Efficacy Evaluable (EE) Population

All subjects who have been entered into the Treatment Phase of the study were reported to have successfully completed treatment, and have been followed successfully until their lesion heals, or until 14 days, whichever is earlier, will be included in the efficacy evaluable (EE) Population. Prior to breaking the study blind, study data will be reviewed to determine which subjects need to be excluded from the EE Population. A subject will be included in a treatment group for analysis based upon the treatment actually administered, rather than the group to which he or she has been assigned. For example, a subject who is randomized to receive a placebo treatment but inadvertently receives an active treatment will be included in the group

receiving an active treatment, and vice versa. Only actual observations will be included in the analyses; no imputation for missing data will be performed. The EE Population will be used for all efficacy analyses.

## **7.2 General Analysis**

All statistical tests will be done using two-sided tests and a Type I error rate of 0.05.

Data listings will be based on all subjects in the Safety Population.

Continuous variables will be summarized using descriptive statistics, specifically the mean, median, standard deviation, minimum and maximum values. Categorical variables will be summarized by frequencies and percentages.

The primary analyses will compare the active treatment group to the placebo control group. Aside from any placebo effect, there should be no efficacy associated with the placebo solution. In addition to the overall analyses, all statistical comparisons will be performed with the subjects stratified based on whether they were treated at erythema (Stage 1) or papule/edema (Stage 2). Inference testing will be completed on efficacy data to compare the groups. Safety data will be summarized with descriptive statistics, but no inference testing will be completed to compare the groups statistically.

## **7.3 Disposition**

The number and percentage of subjects completing the study and terminating early, with the reason for termination, will be summarized for each treatment and overall for the Safety Population. The number of subjects screened, randomized and in each study population will be summarized for each treatment and overall for the Safety Population.

## **7.4 Demographics**

Demographics and baseline characteristics will be summarized with descriptive statistics by treatment and overall for all three analysis populations. For continuous variables, summary statistics (mean, median, standard deviation, minimum, and maximum) will be provided. For categorical variables, the frequency and percent in each category will be presented.

## **7.5 Medical History**

Medical history will be summarized by treatment and overall for all three analysis populations.

## **7.6 Prior and Concomitant Medication**

A listing of concomitant medications will be provided for the Safety Population.

## **7.7 Physical Examinations**

A listing of physical examination findings will be provided for the Safety Population.

## **7.8 Vital Signs**

A listing of vital signs will be provided for the Safety Population.

## 7.9 Pregnancy

A listing of vital signs will be provided for the Safety Population.

## 7.10 Compliance

Estimating compliance with diary data is subjective and often unreliable. Attempts will be made to estimate compliance and calculate confidence intervals. It will be more informative, however, to use individual data rather than summary data. Subject listings with combined data, therefore, will be provided, including: when the clinical lesion assessment reached stage 4, expected number of treatments, actual number of treatments, and time between treatments from the diaries.

## 7.11 Diaries

Diary data will be summarized by treatment group and visit for the Safety Population. Severity (1=none, 2=mild, 3=moderate, 4=severe) and stage (0=prodromal, 1=erythema, 2=papula/edema, 3=vesicle/pustule, 4=ulcer/soft crust, 5=hard crust, 6=residual swelling/dry flaking, 7=normal skin) will be summarized with counts and percentages.

## 7.12 Safety Data

The Safety Population will be used for all summaries of safety data. The safety analysis will be performed on the Safety Population. Assessment of safety and tolerability will be based on AEs. Each AE will be graded with respect to its relationship to treatment using five categories: not related, unlikely, possible, probable, and highly probable. Each AE will also be graded on a three-point severity scale: mild, moderate, and severe. AEs will be coded by body system and preferred term using the Medical Dictionary for Regulatory Activities (MedDRA).

The number and percentage of subjects experiencing treatment emergent adverse events (TEAE) will be tabulated for each treatment group by system organ class (SOC) and preferred term (PT). TEAEs are those occurring on or after first dose of study product. A subject having the same TEAE more than once over the course of the study will be counted only once in the incidence calculation for that TEAE. Similarly, if a subject had more than one TEAE in a SOC, the subject will be counted only once in the total number of subjects with TEAEs for that SOC. The number and percentage of subjects experiencing TEAEs will also be tabulated for those related to treatment (i.e., including possible, probable and highly probable), those that are severe, and those that are serious. If a TEAE is reported more than once for a subject, only the most related event will be counted in the summary for related TEAEs. For the summary of severe TEAEs, if a TEAE is reported more than once for a subject, only the most severe event will be counted in the summary. For the summary of serious TEAEs, if a TEAE is reported more than once for a subject, only the most serious event will be counted in the summary.

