The results of this study found that twelve (12) treatments with Merlin solution, administered 6 hours apart (up to 3 per day) over 96 hours, was generally safe and tolerable in the treatment of subjects with lesions associated with herpes simplex labialis. The majority of treatment-related AEs were classified as mild in intensity. No treatment related AEs in any cohort were classified as severe.

An a priori analysis found that those subjects, who treated with Merlin at first visible signs of a herpetic lesion, erythema, rather than immediately at first symptoms of a herpetic lesion, the prodromal stage, exhibited statistically significant efficacy as compared to placebo for the duration of the classical lesion. The same a priori analysis found trends towards significance for the endpoints of complete healing, duration of the herpetic episode, cumulative lesion size, duration of the hard scab, and the subject assessed severity of lesion pain.

This current clinical study is a follow-up Phase 2 trial using the same Merlin formulation as was used in the studies described above. This trial, as the previous Phase 2 study, will have two treatment arms comparing the safety and efficacy of Merlin solution to that of a placebo (10% ethanol) with treatment at first visible signs of a herpetic episode.

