## **10.6 Safety and Tolerability Analysis**

The safety analysis will be performed on the safety population. Assessment of safety and tolerability will be based on adverse events. Each AE will be graded with respect to its relationship to treatment using five categories: not related, unlikely, possible, probable, and highly probable. Each AE will also be graded on a three-point severity scale: mild, moderate, and severe. Adverse events will be coded by body system and preferred term using the MedDRA (Medical Dictionary for Regulatory Activities) dictionary.

The number and percentage of subjects experiencing adverse events will be tabulated for each treatment group by body system and preferred term. The number and percentage of subjects experiencing AEs will also be tabulated by relationship to drug treatment and by severity. If an AE is reported more than once for a subject, only the most related event will be counted in the analysis by relationship to drug treatment. For the analysis by severity, if an AE is reported more than once for a subject, only the most severe event will be counted in the analysis.

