## 8 Handling of Missing Data

All missing data will be queried. Missing efficacy data on duration endpoints for subjects in the MITT Population which are not retrievable through queries will be handled using imputation of 336 days. Other missing data, including missing safety data, will not be imputed.

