## **9 Changes from the Protocol**

No changes in the analyses described in the original protocol or subsequent amendments are planned. If changes are made prior to unblinding, this document may be amended and such changes will be described. Changes made after unblinding will be noted in the clinical study report.

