## 10 Tables

Disposition

Demographics – Safety

Demographics – MITT

Demographics – EE

Medical History – Safety

Medical History – MITT

Medical History – EE

Efficacy – Duration Endpoints – MITT

Efficacy – Duration Endpoints – EE

Efficacy – Prevention of Progression – MITT

Efficacy – Prevention of Progression – EE

Efficacy – Area Endpoints – MITT

Efficacy – Area Endpoints – EE

Efficacy – Pain Severity – MITT

Efficacy – Pain Severity – EE

Summary of Subjects with TEAEs – Safety

Occurrence of TEAEs by SOC and PT – Safety

Occurrence of TEAEs Related to Treatment by SOC and PT – Safety

Occurrence of Severe TEAEs by SOC and PT – Safety

Occurrence of Serious TEAEs by SOC and PT – Safety

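### SAP 7.12 replaces the protocol's adverse-event summaries by relationship and by severity with related, severe and serious subsets, without declaring it, so mild and moderate events cannot be told apart by arm

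*SAP*

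**What the plan says.** Protocol 10.6 (Safety and Tolerability Analysis) has every adverse event rated on five relationship categories and three severity grades. It asks for a tabulation by body system and preferred term for each treatment group, and then: "The number and percentage of subjects experiencing AEs will also be tabulated by relationship to drug treatment and by severity". It also gives counting rules for repeated events. In the severity summary, "only the most severe event will be counted in the analysis"; a parallel rule keeps the most related event in the relationship summary.

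SAP 7.12 (Safety Data) repeats both rating scales and keeps the table of all TEAEs by organ class, preferred term and arm. For the further breakdowns of subjects with TEAEs, its text reads: "also be tabulated for those related to treatment (i.e., including possible, probable and highly probable), those that are severe, and those that are serious".

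SAP Section 10 (Tables) lists five adverse-event tables: an overall summary of subjects with TEAEs, all TEAEs, related TEAEs, "Occurrence of Severe TEAEs by SOC and PT", and serious TEAEs. SAP Section 9 states: "No changes in the analyses described in the original protocol or subsequent amendments are planned".

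**The concern.** The SAP drops two summaries that the protocol promises and says that it changes nothing. A programmer who follows the SAP would not produce them, and a reader of SAP Section 9 would not know that they had gone.

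The grade kept for separate display is also the one that told least about treatment-related events last time. Of the previous Phase 2 study, Protocol Section 2 reports: "No treatment related AEs in any cohort were classified as severe". It adds that most treatment-related events were mild. By the definitions in Protocol Section 8, the line between mild and moderate is whether the event interferes with everyday activities. That is a natural tolerability question for an acidic solution meant for over-the-counter sale. Adverse events are the only safety endpoint (SAP 6.2) and no safety testing is planned (SAP 7.1.1 and 7.2), so the descriptive tables are the whole comparison of safety between arms.

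**Working it through.** The plan gives no figure to reproduce. The check sets the two documents side by side and asks what can be recovered from the tables that the SAP requires.

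1. **Same events in both documents.** The protocol speaks of adverse events and the SAP of TEAEs. Protocol Section 8 does not capture pre-treatment events on the case report form, so the two terms cover the same events and do not explain the difference.

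2. **What is tabulated, by arm.**

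| Summary | Protocol 10.6 | SAP 7.12 and Section 10 |
|---|---|---|
| All events by organ class and preferred term | Yes | Yes |
| By severity | Mild, moderate, severe | Severe only |
| By relationship | Five categories | Possible, probable and highly probable pooled as related |
| Serious events | Not named | Yes |

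3. **What can be recovered.** For a given preferred term and arm, let A be the number of subjects with any TEAE, S the number with a severe one and R the number with a related one. If every event carries both ratings:
   - mild + moderate (worst grade) = A − S
   - possible + probable + highly probable (closest relationship) = R
   - not related + unlikely = A − R

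   The first line is one equation in two unknowns, so mild and moderate cannot be separated. Of the three grades, one is shown alone and two are pooled. Of the five relationship categories, none is shown alone: three are pooled in R and two in A − R. The serious table does not help, because seriousness is defined by outcome and not by grade.

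4. **Under the previous study's experience.** If treatment-related events again include no severe ones, the severe table contains no treatment-related events. No required table then grades any of them.

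5. **Other places where grade might appear.** The overall summary of subjects with TEAEs has a title but no defined contents. It could hold a severity split, but nothing requires one. Safety Population listings may show the grade of individual events, but they are not counts and percentages by arm. The severity summary in SAP 7.11 concerns diary pain scores, not adverse-event grades.

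6. **Signs of loose drafting.** SAP 7.12 retains the most-severe and most-related counting rules. In a table limited to severe events, choosing the most severe does almost nothing. The rules fit the full breakdowns in the protocol, which suggests that the reduction was not a considered decision.

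**The case against.** The strongest reply is that little is lost. All TEAEs are still counted by arm and preferred term, and those judged possible or closer are counted again in the related table. An excess of application-site reactions on active treatment would be visible in both. The grades are still collected, listings are planned for the whole Safety Population, no safety inference depends on these tables, and the missing summaries could be produced after database lock. All of this stands, and it limits the point to the missing breakdowns and the undeclared change.

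Several stronger readings are tempting, and the documents do not support them.

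- A reader might infer that mild and moderate reactions would not be tabulated at all. They would be, as part of the all-TEAE table; only the split is missing.
- A reader might infer that the severe table will be nearly empty. The statement about the previous study covers treatment-related events only, whereas the SAP's table takes severe TEAEs of any cause.
- A reader might infer that moderate irritation is the expected toxicity. The pilot study is described as showing very mild irritation in three subjects and mild burning in one. Moderate treatment-related events in the previous Phase 2 study are at most implied, by a majority being mild and none severe. The documents give no rate for them.
- A reader might infer that the protocol promised organ class and preferred term crossed with grade. Protocol 10.6 gives these tabulations in separate sentences, so a simple summary by grade and by category would satisfy it.
- SAP Section 8 says "Other missing data, including missing safety data, will not be imputed", and a reader might infer that events without a rating would be lost. Missing data are queried first, and an event with an unresolved rating still counts in the all-TEAE table. Neither document has a rule that counts missing ratings as related or severe, so such a rule would not restore anything in the protocol.

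**Conclusion.** The point holds as an undeclared difference between protocol and SAP in the reporting of the only safety endpoint. Two summaries specified in the protocol are missing from the SAP, and the no-change statement in SAP Section 9 is therefore incorrect. The consequence is that mild and moderate events are counted by arm but cannot be told apart in any table the SAP requires, and the relationship categories appear only as pooled groups.

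The severity is minor. No hypothesis test, efficacy result or data collection is affected. The conclusion rests on comparing the two texts and needs no assumption about event rates. It does assume that the overall TEAE summary, whose contents are undefined, will not happen to include a breakdown by grade and by relationship category.

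**What to change.** In SAP 7.12 and Section 10, add two summaries of the number and percentage of subjects with TEAEs for each arm:

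- by maximum severity: mild, moderate, severe
- by closest relationship: not related, unlikely, possible, probable, highly probable

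A breakdown by organ class and preferred term is optional. The counting rules already in SAP 7.12 can be applied to these summaries. Keep the related, severe and serious tables as they are.

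If the sponsor prefers the shorter set, state the reduction and the reason for it in SAP Section 9.

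The cost is two descriptive tables from ratings already collected, or a short statement in Section 9. No new data are needed.

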## 7.13 Efficacy Analyses

The efficacy analysis will be performed on both the MITT and the EE Populations; and stratified based on whether they were treated at erythema (Stage 1) or papule/edema (Stage 2). Groups will be compared at each visit for which the endpoint of interest is captured.

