
Statistical Methods: Generally, statistical hypothesis tests will be two-tailed, and statistical significance will be declared when the p-value is less than 0.05. Continuous variables will be summarized using descriptive statistics, specifically the mean, median, standard deviation, minimum and maximum. Categorical variables will be summarized by frequencies and percentages.
 
All subjects who received (at least some) treatment, whether they were formally entered into the Treatment Phase of the study or applied the test material without formal authorization, will be included in the Safety Population. The safety analysis will be performed on the Safety Population.
 
All subjects who have been entered into the Treatment Phase of the study will be included in the Modified Intent to Treat (MITT) population. The MITT population will be used as the primary analysis population. All subjects who have been entered into the Treatment Phase of the study and have been followed successfully until their lesion healed, or until 14 days, whichever is earlier, will be included in the Efficacy Evaluable population. The efficacy analysis will be performed on both the MITT and the Efficacy Evaluable populations.
 
No imputation of missing data will be performed for the efficacy analyses for the Efficacy Evaluable population.
 
The duration of the classical herpetic lesion (both clinician and patient assessed) will be analyzed using the Hodges-Lehmann method as the primary efficacy analysis method for estimating the median difference between the two arms. Duration of the herpetic episode (both clinician and patient assessed), duration of complete healing of the herpetic episode (both clinician and patient assessed), duration of the herpetic lesion (both clinician and patient assessed), duration of the herpetic lesion hard scab (both clinician and patient assessed), and duration of pain will be analyzed in the same manner as the duration of the classical lesion.
 
The proportions of subjects in each treatment group who do not display classical lesions (prevention of progression to classical lesions) will be compared using Fisher's Exact Test.
 
For pain, the maximum severity will be analyzed using the Cochran-Mantel-Haenszel Test to test for differences between treatment groups.
		

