#### **10.7.8 Severity of Lesion Pain**

The maximum severity (over time) of lesion pain will be summarized.

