**Cumulative lesion area of all lesions:** Cumulative lesion area of all lesions is defined as the cumulative lesion area of both classical and non-classical recurrences.

**Duration of classical herpetic lesion hard scab:** Duration of classical herpetic lesion hard scab will be defined as the assessed duration of the hard crust, stage 5, for the classical lesions. This duration will represent the onset of stage 5 until the time of classical lesion healing at stage 6 or 7, whichever occurs earlier. For lesions that bypass stage 5, duration of hard scab phase will be calculated as time between the two adjacent assessments either side of stage 5.

**Severity of lesion pain:** Pain will be evaluated based on the subject's diary, where the subject will record, just prior to each treatment and three times daily once treatment is complete, the level of pain caused by the defined lesion. The rating scale for pain assessment has four levels for severity: none (1), mild (2), moderate (3), and severe (4).

**Duration of lesion pain:** Duration of pain will be measured in hours from the time of the first occurrence of a pain level of mild, moderate, or severe until a consistent score of a pain level of none has been achieved over at least 2 consecutive pain assessments, or until the lesion is completely healed, whichever occurs first. Subjects who do not reach the no-pain level within 14 days will be considered censored immediately following their last pain assessment. Subjects who never reach a pain level of mild, moderate, or severe will be assigned a duration of pain value of 0 hours.

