### **7.13.4 Pain Severity**

For pain severity, counts and percentages will be summarized for all levels of severity, and Cochran-Mantel-Haenszel tests will be used to compare the groups.

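### The SAP drops the protocol's per-subject maximum for pain severity and calls for comparison at each visit, which allows repeated unadjusted tests that at later visits cover only unhealed subjects

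*SAP*

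**What the plan says.** Protocol Section 1 (Statistical Methods) fixes both the summary and the test: "For pain, the maximum severity will be analyzed using the Cochran-Mantel-Haenszel Test to test for differences between treatment groups". Protocol Section 10.7.8 repeats the summary: "The maximum severity (over time) of lesion pain will be summarized". Each subject therefore contributes one value.

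SAP Section 6.1.4 defines severity of lesion pain only as the four-level diary score. It names no maximum, no other per-subject summary and no time point. SAP Section 7.13.4 then states: "For pain severity, counts and percentages will be summarized for all levels of severity, and Cochran-Mantel-Haenszel tests will be used to compare the groups". The only timing rule in the efficacy section is the general one in Section 7.13: "Groups will be compared at each visit for which the endpoint of interest is captured". Protocol Section 10.7 has no such rule.

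On the error rate, SAP Section 7.2 says "All statistical tests will be done using two-sided tests and a Type I error rate of 0.05" and describes no adjustment for multiple tests. The analysis matrix in Section 7.13.5 specifies no imputation for pain severity and repeats every analysis overall, for Stage 1 and for Stage 2, in both the MITT and EE populations. SAP Section 9 says that no changes from the protocol's analyses are planned.

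**The concern.** The two documents do not describe the same pain severity analysis, and the SAP does not say so. An analyst working from the SAP alone has a repeated ordinal score, a CMH test and an instruction to compare groups at each visit. The obvious result is one test per visit. Pain is scored three times a day in the diary, and the SAP does not say which score stands for a visit.

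Two things are at stake. First, up to 14 tests at 0.05 replace one, with no adjustment and no visit named as decisive. Second, after the minimum follow-up to Visit Day 3, a subject leaves the data once the lesion heals. Late visits then compare the unhealed part of each arm, and healing is what the treatment is meant to change. Those subsets are not the randomised groups.

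**Working it through.** The documents give no figure for by-visit pain tests, so there is no stated figure to reproduce.

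**Step 1: who is observed at a visit.**
- Clinic visits run daily to Stage 7 or Day 14, with a minimum of three consecutive days (SAP 2.2; Protocol 7.3).
- The pain diary runs until the lesion is healed (Protocol 7.2.5 and 7.2.5.1) or until the final clinic visit (SAP 2.2).
- Pain severity is not imputed (SAP 7.13.5 and 8), so a healed subject is absent rather than scored as 'none'.

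Up to about Visit Day 3 all treated subjects are due for assessment. After that only unhealed subjects remain.

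**Step 2: number of tests.** Two populations × three sets (overall, Stage 1, Stage 2) = 6 tests if each subject has one value. With up to 14 visits, 6 × 14 = 84.

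**Step 3: chance of at least one p<0.05 with no treatment effect, within one population and stratum.** If the tests were independent, this is 1 − 0.95^k: 1 − 0.95^8 = 33.7% and 1 − 0.95^14 = 51.2%. These are upper figures, because visits on the same subjects are correlated. For correlated visits I let the test statistics follow Z(1) ~ N(0,1) and Z(k) = ρ·Z(k−1) + √(1 − ρ²)·e(k), and estimated P(any |Z(k)| > 1.96) from 1,000,000 simulated sequences. The documents give no correlation, so ρ is an assumption shown over a range:

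| ρ (assumed) | 8 visits | 14 visits |
|---|---|---|
| 0.5 | 29.8% | 45.8% |
| 0.8 | 21.3% | 32.7% |
| 0.95 | 12.4% | 17.2% |

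A separate subject-level simulation used 75 per arm, 14 daily visits, a CMH row-mean-score test and exit at healing. Its assumptions are a median healing time of 8 days with log-SD 0.4, pain falling as the lesion heals, and correlation of the latent pain score between adjacent visits of 0.5, 0.8 or 0.95. It gave 44%, 35% and 27% over 14 visits. One test of each subject's maximum gave 4.7% to 5.3%. Any single visit stayed at 4% to 5%, so the inflation comes from repetition.

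**Step 4: what late visits can detect.** This uses the same simulation with correlation 0.8.

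*Treatment only speeds healing (time ratio 0.8, assumed):*

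| Visit | Still observed, active / placebo (of 75) | Power, unhealed only | Power, healed counted as 'none' |
|---|---|---|---|
| 8 | 31 / 47 | 6% | 31% |
| 9 | 22 / 37 | 5% | 32% |
| 10 | 15 / 29 | 4% | 31% |

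*Treatment lowers pain directly (latent shift 0.4, assumed):* power at visit 1 is 49% either way, and at visit 8 it is 26% in unhealed subjects against 21% with healed subjects as 'none'. The loss therefore arises at later visits and when benefit comes through faster healing.

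The maximum has power of about 11% in the faster-healing case and about 50% in the direct-effect case. It does not recover a pure healing effect, which the duration endpoints measure.

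**The case against.** The strongest reply is that the SAP is loosely worded and does not plan 14 tests.
- Protocol Section 10.7 itself omits the maximum in its sentence on severity endpoints, and SAP 7.13.4 closely follows it.
- SAP Section 9 says that the protocol's analyses stand, which supports reading the maximum back in.
- SAP Section 7.11 already summarises diary severity by visit, without a test.
- The SAP's table list has one pain severity title per population, none marked by visit.

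All of this stands, and it shows that the SAP is inconsistent with itself. It does not remove the sentence in 7.13, which is the only timing rule in the efficacy section and has no counterpart in the protocol's.

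A reader might also infer that lesion area would be tested at every visit, since size is measured at each visit. The documents do not support that. SAP 6.1.4 defines one maximum and two cumulative areas, each one value per subject, and no by-visit area endpoint.

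Nor do they support a general claim that real effects would be hidden. Follow-up to Visit Day 3 keeps early visits free of selection by healing, and a direct effect on pain is not lost (Step 4).

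Finally, the consequence is modest. The SAP lists pain severity among the other, diary-based endpoints. Protocol 10.2.1 also lists a clinician-assessed pain item as secondary, but the protocol describes only subject-reported pain and the SAP does not carry that item.

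**Conclusion.** The point holds for pain severity only. The SAP omits the protocol's per-subject maximum, adds a by-visit comparison rule and declares no change. Followed literally, it allows up to 14 unadjusted CMH tests per population and stratum. The chance of at least one false positive is then about 12% to 30% over 8 visits and 17% to 46% over 14, against about 5% for one test of the maximum. These ranges rest on assumed adjacent-visit correlations of 0.5 to 0.95. The late-visit power figures rest on assumed healing and pain models and show direction, not expected values.

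It would go too far to conclude that the SAP clearly prescribes by-visit testing. The wording permits it, while other parts of the SAP point the other way. The primary endpoint, the other durations, progression and the area endpoints are one value per subject and are unaffected. The discrepancy should be corrected before unblinding, but it does not threaten the trial's main conclusion.

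**What to change.** In SAP 6.1.4 and 7.13.4, define pain severity as each subject's maximum diary score over the Treatment Phase, as in Protocol Sections 1 and 10.7.8. Test it once by CMH in each population and each planned stratum (6 tests in all). In SAP 7.13, delete the by-visit sentence, or limit it to descriptive displays in which healed subjects are shown as 'none' so that the displays do not carry the same selection. If by-visit testing is intended, list it in SAP Section 9 as a change from the protocol.

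The cost is SAP wording only: no new data and fewer analyses. SAP Section 9 already provides for amendment before unblinding.
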